1.2 OBJECTIVES AND ENDPOINTS

Table 1 - Objectives and endpoints

Objectives	Endpoints
Primary	

 • To evaluate the efficacy of different doses of amlitelimab compared to placebo in participants with moderate-to-severe, uncontrolled asthma. 	
 • Annualized rate of severe exacerbation events over 48 weeks, defined as: 
 - Worsening of asthma requiring the use of systemic corticosteroids for ≥ 3 days or, in the case of a stable maintenance regimen of oral corticosteroids (OCS) for the treatment of

Objectives	Endpoints
	asthma, a doubling of the dose for 3 or more days; or
	- Hospitalization or emergency room visit because of asthma, requiring systemic corticosteroids
Secondary	

 To evaluate the effects of amltelimab compared to placebo on lung function as measured by forced expiratory volume in 1 second (FEV1) To evaluate the effects of amltelimab on Asthma Control Questionnaire 5 (ACQ-5) To evaluate the effects of amltelimab on time to first severe exacerbation event To evaluate the effects of amltelimab on other spirometry assessments To evaluate the effects of amltelimab on fraction of exhaled nitric oxide (FeNO) To evaluate the effects of amltelimab compared to placebo on reducing the incidence of "loss of asthma control" (LOAC) events To evaluate the effects of amltelimab on time to first LOAC event To evaluate the effects of amltelimab on asthma symptoms 	
 Change from baseline in pre-bronchodilator (BD) FEV1 at Week 48 (key secondary endpoint) Change from baseline in post-BD FEV1 at Week 48 The absolute change in the percent predicted FEV1 from baseline to Week 48 (pre-BD and post-BD) Change from baseline in ACQ-5 score at Week 48 (key secondary endpoint) Change from baseline in ACQ-5 score at Weeks 2, 4, 8, 12, 24, 36, and 60 Time to first severe exacerbation event Change from baseline in pre-BD and post-BD FEV1 and other lung function measurements (peak expiratory flow [PEF], forced vital capacity [FVC], and forced expiratory flow [FEF] 25-75%) at each spirometry endpoint Change from baseline in FeNO at Weeks 2, 4, 8, 12, 16, 24, 36, 48 and 60 Annualized rate of LOAC events, during 48 weeks of treatment, defined by one or several of the following criteria: 
 A 30% or greater reduction from baseline in morning PEF on 2 consecutive days ≥6 additional reliever puffs of short-acting beta 2-agonists (SABA) OR ≥4 additional puffs of low-dose ICS/formoterol in a 24-hour period (compared to baseline) on 2 consecutive days Increase in ICS ≥4 times than the Visit 2 dose Worsening of asthma requiring the use of systemic corticosteroids for ≥3 days or, in the case of a stable maintenance regimen of OCS for the treatment of asthma, a doubling of the dose for 3 or more days Hospitalization or emergency room visit because of asthma, requiring systemic corticosteroids severe exacerbation event Time to first LOAC event Change from baseline in the Asthma Daytime Symptom Diary (ADSD) 6-item daily morning score and in the Asthma Nighttime Symptom Diary (ANSDD) 6-item daily evening scores at Weeks 2, 4, 8, 12, 24, 36, 48, and 60

Objectives	Endpoints

 To evaluate the effects of amltelimab on reducing the incidence of severe asthma exacerbations requiring hospitalization or emergency room or urgent care visit Assess the effect of amltelimab on BD therapy To evaluate the pharmacokinetics (PK) of amltelimab and anti-drug antibodies to amltelimab in participants with asthma To evaluate the safety of amltelimab in participants with asthma To evaluate the effects of amltelimab on participant reported outcomes (PROs) To evaluate the effects of amltelimab on ACQ-6 and ACQ-7 	
 Annualized rate of severe asthma exacerbations requiring hospitalization or emergency room or urgent care visit during 48 weeks of treatment Change from baseline in the numbers of inhalations/day of SABA or low-dose ICS/formoterol for symptom relief at Weeks 2, 4, 8, 12, 24, 36, 48, and 60 Serum amltelimab concentrations measured throughout the study Incidence of anti-amltelimab antibody positive response Percentage of participants with treatment-emergent adverse events (TEAEs), including local reactions, adverse events of special interest (AESIs), serious adverse events (SAEs) Incidence of potentially clinically significant laboratory test, vital signs, and ECG abnormalities in the treatment period Change from baseline in Asthma Quality of Life Questionnaire with Standardized Activities (AQLQ (S)) Self-Administered Score at Week 48 (key secondary endpoint) AQLQ (S) Self-Administered Score at Weeks 2, 4, 8, 12, 24, 36, and 60 Change from baseline in St. George's Respiratory Questionnaire (SGRQ) at Weeks 2, 4, 8, 12, 24, 36, 48, and 60 Proportion of participants with a decrease from baseline of at least 4 points in SGRQ total score at Week 48 Change from baseline in ACQ-6 score and ACQ-7 at Weeks 2, 4, 8, 12, 24, 36, 48, and 60
Tertiary/Exploratory	

 

 

 

 
 
 

 

 

 
	
 

 

 

 
 
 

 

 

 

1.2.1 Estimands

Page 10

Table 2 - Summary of primary estimand for the primary endpoint and key secondary efficacy endpoints

Endpoint Category (estimand)	Estimands			
	Endpoint	Population	Intercurrent event(s) handling strategy	Population-level summary (Analysis and missing data handling)
Primary objective: To evaluate the efficacy of different doses of amltelimab compared to placebo in participants with moderate-to-severe, uncontrolled asthma.				
Primary endpoint Primary estimand (treatment policy)	Annualized rate of severe exacerbation events over 48 weeks	ITT	
The following IEs may occur:
 
 1. Taking prohibited rescue medications or procedures post randomization. 2. Early discontinuation of study treatment due to lack of efficacy without taking prohibited rescue medication or procedure. 3. Early discontinuation of study treatment due to other reason without taking prohibited rescue medication or procedure. 
The IEs will be handled as follows:
 
All three IEs above will be handled with treatment policy strategy. For participants who take rescue medication or procedure, or discontinue IMP due to any reason on or before Week 48, all severe asthma exacerbation events up to Week 48 will be included in the analysis irrespective of study treatment adherence or use of rescue medications and procedures; for participants who withdraw from the study prior to Week 48, the observation duration will be from randomization to Week 48 or to the last contact date, whichever is earlier.
	
 • Estimated annualized event rate for each study intervention group and the corresponding 2-sided 95% confidence interval (CI). • The event risk ratio (RR) of each amltelimab regimen versus placebo, and the corresponding 2-sided 95% CI and p-value. 
The annualized rate of severe asthma exacerbation will be analyzed using a negative binomial regression model. The model will include the total number of severe asthma exacerbation events that occur over 48 weeks as the response variable, with study intervention group, region (pooled country), screening eosinophil strata (<300 cells/μL or ≥300 cells/μL), number of asthma exacerbations in the previous 12 months strata (=1 or >1) and baseline ICS dose level (categorical variable) as covariates. Log-transformed observation duration will be the offset variable.
 
Missing data handling:
 
To account for a shorter duration of follow-up of participants with IEs prior to Week 48, the primary analysis negative binomial model will include an offset term for the logarithm of observation duration. No further imputation will be performed for the unobserved asthma events that may happen after study discontinuation and up to Week 48.

Secondary objective: To evaluate the effects of amltelimab compared to placebo on lung function as measured by forced expiratory volume in 1 second (FEV1)				
Key secondary endpoint Primary Estimand (treatment policy)	Change from baseline in pre-bronchodilator (BD) FEV1 at Week 48	ITT	
The following IEs may occur:
 
 1. Taking prohibited rescue medications or procedures post randomization. 2. Early discontinuation of study treatment due to lack of efficacy without taking prohibited rescue 	
 • Mean change from baseline in pre-BD FEV1 at Week 48 by study intervention group. • Difference in the least squares (LS) mean change from baseline in pre-BD FEV1 at Week 48 of each amltelimab regimen versus placebo, and the corresponding 2-sided 95% CI and p-value.

Endpoint Category (estimand)	Estimands			
	Endpoint	Population	Intercurrent event(s) handling strategy	Population-level summary (Analysis and missing data handling)
			
medication or procedure.
 
3. Early discontinuation of study treatment due to other reason without taking prohibited rescue medication or procedure.
 
The IEs will be handled as follows:
 
All three IEs above will be handled with treatment policy strategy. Participants who take rescue medication or procedure, or discontinue IMP due to any reason on or before Week 48 will be asked and encouraged to return to the clinic for all remaining study visits; their pre-BD FEV1 data at Week 48 will be included in the analysis irrespective of treatment adherence or use of prohibited medications and procedures.
	
The change from baseline in pre-BD FEV1 at Week 48 will be analyzed using ANCOVA model. The model will include change from baseline in pre-BD FEV1 value at Week 48 as response variable, and study intervention group, age, sex, height, region (pooled country), screening eosinophil strata (<300 cells/μL or ≥300 cells/μL), number of asthma exacerbations in the previous 12 months strata (=1 or >1), baseline ICS dose level (categorical variable) and the corresponding baseline value (continuous variable) as covariates.
 
Missing data handling:
 
Multiple imputation will be used to impute any missing values at the analysis timepoint (pre-BD FEV1 at Week 48). The multiple imputation will use all participants. Results from each complete dataset will be combined using Rubin's formula to provide the final efficacy results.

Secondary objective: To evaluate the effects of amltelimab on Asthma Control Questionnaire 5 (ACQ-5)				
Key secondary endpoint Primary Estimand (treatment policy)	Change from baseline in ACQ-5 score at Week 48	ITT	
The IEs, IEs handling are defined/described in the same way as those specified for the primary estimand for the key secondary endpoint of "Change from baseline in pre-BD FEV1 at Week 48".
	
 • Mean change from baseline in ACQ-5 score at Week 48 by study intervention group. • Difference in the LS mean change from baseline in ACQ-5 score at Week 48 of each amltelimab regimen versus placebo, and the corresponding 2-sided 95% CI and p-value. 
The key secondary endpoint of change from baseline in ACQ-5 at Week 48 will be analyzed using ANCOVA in the same fashion as for the primary estimand for the key secondary endpoint of "Change from baseline in pre-BD FEV1 at Week 48". The covariates to be included are study intervention group, age, region (pooled country), screening eosinophil strata (<300 cells/μL or ≥300 cells/μL), number of asthma exacerbations in the previous 12 months strata (=1 or >1), baseline ICS dose level (categorical variable) and the corresponding baseline value (continuous variable).
 
Missing data handling:
 
The same missing data handling method as for the key secondary endpoint/primary estimand of "Change from baseline in pre-BD FEV1 at week 48" will be used.

Endpoint Category (estimand)	Estimands			
	Endpoint	Population	Intercurrent event(s) handling strategy	Population-level summary (Analysis and missing data handling)
Secondary objective: To evaluate the effects of amltelimab on participant reported outcomes (PROs)				
Key secondary endpoint Primary Estimand (treatment policy)	Change from baseline in Asthma Quality of Life Questionnaire with Standardized Activities (AQLQ (S)) Self-Administered Score at Week 48	ITT	The IEs, IEs handling are defined/described in the same way as those specified for the primary estimand for the key secondary endpoint of "Change from baseline in pre-BD FEV1 at Week 48".	
 • Mean change from baseline in AQLQ (S) Self-Administered Score at Week 48 by study intervention group. • Difference in the LS mean change from baseline in AQLQ (S) Self-Administered Score at Week 48 of each amltelimab regimen versus placebo, and the corresponding 2-sided 95% CI and p-value. 
The key secondary endpoint of change from baseline in AQLQ (S) Self-Administered Score at Week 48 will be analyzed using ANCOVA in the same fashion as for the primary estimand for the key secondary endpoint of "Change from baseline in pre-BD FEV1 at Week 48". The covariates to be included are study intervention group, age, region (pooled country), screening eosinophil strata (<300 cells/μL or \geq300 cells/μL), number of asthma exacerbations in the previous 12 months strata (=1 or >1), baseline ICS dose level (categorical variable) and the corresponding baseline value (continuous variable).
 
Missing data handling:
 
The same missing data handling method as for the key secondary endpoint/primary estimand of "Change from baseline in pre-BD FEV1 at week 48" will be used.

2 ANALYSIS POPULATIONS

[Redacted]

Table 3 - [Redacted]

[Redacted Table Content]

[Redacted]

[Redacted]

[Redacted]

[Redacted]

3.1 GENERAL CONSIDERATIONS

[illegible]

Medication	Action to IMP	Intervention in the main statistical analysis	Selection criteria
Anti-IL4R mAb (eg, dupilumab [Dupixent®])	IMP discontinuation	Yes	CDGsn00521
Anti-IL5 or IL-5R mAb (eg, benralizumab [Fasenra], mepolizumab [Nucala], or reslizumab [Cinqair])	IMP discontinuation	Yes	CDGsn00521
Anti-IgE mAb (eg, omalizumab [Xolair])	IMP discontinuation	Yes	CDG00486

Medication	Action to IMP	Intervention in the main statistical analysis	Selection criteria
Anti-TSLP mAb (eg, Tezepelumab [Tezspire®])	IMP discontinuation	Yes	CDGsn00521
Bronchial thermoplasty	IMP discontinuation	Yes	CMQ20097
Initiation of continuous oral corticosteroid treatment during the study beyond 14 days consecutively	IMP discontinuation	Yes	CDGsn00010 with route = 'oral' and treatment duration beyond 14 days consecutively

3.2 PRIMARY ENDPOINT(S) ANALYSIS

3.2.1 Definition of endpoint(s)

[REDACTED]

[REDACTED]

[REDACTED]

3.2.2 Main analytical approach

[REDACTED]

[REDACTED]

[REDACTED]

[REDACTED]

[REDACTED]

3.2.4 [REDACTED]

[REDACTED]

[REDACTED]

[REDACTED]

[REDACTED]

[REDACTED]

[illegible]

[REDACTED]
 [REDACTED]
 [REDACTED]

[REDACTED]
 [REDACTED]
 [REDACTED]
 [REDACTED]
 [REDACTED]

3.3 SECONDARY ENDPOINT(S) ANALYSIS

[REDACTED]

3.3.1 Key/Confirmatory secondary endpoint(s)

3.3.1.1 Definition of endpoint(s)

[REDACTED]

[REDACTED]

[REDACTED]

3.3.1.2 Main analytical approach

[REDACTED]

[REDACTED]
 [REDACTED]
 [REDACTED]
 [REDACTED]
 [REDACTED]
 [REDACTED]
 [REDACTED]

Age Group	Percentage of Respondents
18-29	80%
30-49	75%
50-64	70%
65+	60%

[illegible]

[illegible]

3.3.1.3 [REDACTED]

[REDACTED]
 [REDACTED]
 [REDACTED]

[illegible][illegible]

[REDACTED]

Government	Percentage
Current government	85%
Previous government	15%

[REDACTED]
 [REDACTED]
 [REDACTED]
 [REDACTED]
 [REDACTED]
 [REDACTED]
 [REDACTED]

[REDACTED]

[REDACTED]

[REDACTED]

[illegible]

[REDACTED]

[REDACTED]
[REDACTED]

[REDACTED]
[REDACTED]

[REDACTED]
[REDACTED]
[REDACTED]

[REDACTED]
[REDACTED]
[REDACTED]

[REDACTED]
[REDACTED]
[REDACTED]

[REDACTED]

[illegible][illegible]

[REDACTED]

[REDACTED]

[REDACTED]

[REDACTED]

[REDACTED]

[REDACTED]

[REDACTED]

[REDACTED]

[REDACTED]

[REDACTED]
 [REDACTED]
 [REDACTED]
 [REDACTED]
 [REDACTED]
 [REDACTED]
 [REDACTED]

[REDACTED]
 [REDACTED]
 [REDACTED]
 [REDACTED]
 [REDACTED]
 [REDACTED]

_____.

[illegible]

Bar Index	Approximate Length (%)
1	100
2	95
3	70
4	100
5	92
6	98
7	100
8	25
9	100
10	98
11	100
12	20

Table 5 - [REDACTED]

3.6.1 Extent of exposure

The extent of IMP exposure will be assessed by the duration of IMP exposure and compliance and summarized within the safety population.

Duration of IMP exposure

Duration of IMP exposure is defined as last IMP administration date – first IMP administration date +28 days, if the last IMP is prior to Week 24; and as last IMP administration date – first IMP administration date +84 days, if the last IMP is on or after Week 24, regardless of unplanned intermittent discontinuations. If the date of the last dose of IMP is missing, the duration of IMP will be left as missing.

Duration of IMP exposure will be summarized descriptively as a quantitative variable (number, mean, SD, median, minimum, and maximum). In addition, duration of treatment exposure will also be summarized categorically by numbers and percentages for each of the following categories and cumulatively according to these categories:

- 0 and \leq 8 weeks
- > 8 and \leq 16 weeks
- > 16 and \leq 24 weeks
- > 24 and \leq 36 weeks
- > 36 and \leq 48 weeks
- > 48 weeks

Additionally, the cumulative duration of treatment exposure (expressed in participant-years) will be provided.

[REDACTED]

[REDACTED]
[REDACTED]
[REDACTED]

[REDACTED]
[REDACTED]
[REDACTED]
[REDACTED]

[REDACTED]

[illegible]

Table 6 - [REDACTED]

Table 7 - [REDACTED]

1. *Journal of the American Medical Association*, 2000; 283: 2689-2693.

████████████████████

██████████

██████████

[REDACTED]

[REDACTED]

3.6.4 [REDACTED]

[illegible]

[REDACTED]

3.7 OTHER ANALYSES

3.7.1 Other variables and/or parameters

3.7.1.1 PK analyses

[REDACTED]

[REDACTED]

[REDACTED]

[REDACTED]

[REDACTED]

[REDACTED]

[REDACTED]

[illegible]

[REDACTED]
 [REDACTED]
 [REDACTED]

[REDACTED]
 [REDACTED]
 [REDACTED]

[REDACTED]
 [REDACTED]
 [REDACTED]
 [REDACTED]
 [REDACTED]
 [REDACTED]
 [REDACTED]

[illegible]

[REDACTED]

[REDACTED]

[REDACTED]

[REDACTED]

[REDACTED]

[REDACTED]

[REDACTED]

[REDACTED]

[REDACTED]

[REDACTED]

3.8 INTERIM ANALYSES

An interim analysis (IA) is planned to be performed when all randomized participants have completed at least 24 weeks of visit.

The purpose of the IA is to obtain early information for the planning of the Phase 3 program and to use the IA efficacy and safety data in health authority interaction. No alpha will be spent on the interim analysis as the analysis results will not make an early claim on the treatment effect of amltelimab for efficacy endpoints and the study will continue unchanged irrespective of the interim analysis results. The full alpha will be spent on the primary analysis for this dose-finding study.

In order to maintain the further double-blinded conduct of the study, a separated unblinded team (IA team) will be setup to perform the IA. Any unblinded results or information will be strictly limited within the IA team, and any person being unblinded will no longer being involved in study operation and management to protect the study integrity. Participants, sites and study vendors, study operation and management team will remain blinded and will not have any access to the unblinded study folders or IA analysis results.

The *IA data cutoff date* is April 22nd, 2024, which is the date when all randomized subjects completed at least 24 weeks visit.

The **primary analysis population** for the interim analysis will be the ITT/randomized population. The analysis of the endpoints (provided below) will use all the data collected for this primary analysis population prior to the *IA data cutoff date*, including those who may have withdrawn from the study prior to Week 24.

There are two **secondary analysis populations** for the analyses of the primary endpoint:

1. **Week 48 analysis set:** it includes the participants who were randomized in the study early enough that the participant could have the opportunity to complete at least 48 weeks of treatment at the *IA data cutoff date*, including those who may have withdrawn from the study prior to Week 48.
2. **Week 60 analysis set:** it includes the participants who were randomized in the study early enough that the participant could have the opportunity to complete the entire 60-week

treatment period at the *IA data cutoff date*, including those who may have withdrawn from the study prior to Week 60.

The below parameters will be evaluated for the primary analysis population only:

- Participant disposition
- Demographics and baseline characteristics
- Medical history and comorbidities
- Prior & Concomitant Medications and procedures

The below parameters will be evaluated for the safety, PK/ADA or biomarker population only:

- The extent of exposure to investigational product and compliance
- Adverse events
- Laboratory values, ECG, vital signs
- PK/ADA

██████████

The below parameters will be evaluated for the primary analysis population, and the two secondary analysis populations, separately:

- Analysis of the annualized rate of adjudicated severe asthma exacerbations: The annualized event rate for each study intervention group, the ratio of the rates and relative rate reductions between each amltelimab dosing regimen and placebo, and the corresponding 95% CI and p-values will be provided.
 - annualized rate of adjudicated severe asthma exacerbations prior to the *IA data cutoff date* up to Week 48 (primary analysis population)
 - annualized rate of adjudicated severe asthma exacerbations prior to Week 48 (Week 48 analysis set)
 - annualized rate of adjudicated severe asthma exacerbations prior during 60-weeks treatment period (Week 60 analysis set)
- Analysis of the change from baseline in pre-BD FEV1, ACQ-5 score and AQLQ(S): Descriptive statistics including number of patients, mean, standard error and LS mean for each treatment group will be obtained. Differences in the LS means, and 95% CIs and p-values of the differences will be provided for comparison between each amltelimab dosing regimen and placebo will be provided.
 - Change from baseline pre-BD FEV1, ACQ-5 score and AQLQ(S) at Week 24 (primary analysis population)
 - Change from baseline in pre-BD FEV1, ACQ-5 score and AQLQ(S) at Week 48 (Week 48 analysis set)

- Change from baseline in pre-BD FEV1, ACQ-5 score and AQLQ(S) at Week 60 (Week 60 analysis set)

Other efficacy parameters, eg, including but not limited to post-BD FEV1, ACQ-6 score, FeNO, LOAC, etc. will also be analyzed on the primary analysis population.

Analysis of the annualized rate of severe asthma exacerbations and the annualized rate of LOAC prior to the *IA data cutoff date* up to Week 48, and analysis of the change from baseline in pre-BD FEV1, ACQ-5, AQLQ(S), and FeNO at Week 24 will be performed on the primary analysis population by subgroups listed in [Section 3.6.4](#).

Analyses methods and conventions described in the other sections of this SAP will be applied for all analyses as applicable. The following additional rules will apply for analyses performed at interim analysis:

- Participants without end of treatment visit performed at the time of the cut-off date will be considered as ongoing and exposed up to the cut-off date. Therefore:
 - Participants who did not complete treatment period nor prematurely discontinued the study intervention at cut-off date will be analyzed as “ongoing” in the disposition summary.
 - Their TE period, treatment period and concomitant medication period will end at the cut-off date.
 - Their treatment duration will be derived by considering date of cut-off as last IMP date.
- Analyses of number of IMP administration and compliance will be performed up to the last IMP administration reported in the e-CRF up to the cut-off date.

AEs occurring, worsening or becoming serious after the cut-off date will not be included in the analyses. However, any available outcome before database lock, regardless of timing in relation to the cut-off date, of an AE starting prior to the cut-off date will be taken into account. Medications, intervention discontinuations/completions and deaths occurring after the cut-off date will not be included in the analyses.

[illegible]

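### At the interim, SAP 3.8 and 3.6.1 applied as written credit each ongoing participant with 84 days of exposure beyond the data cut-off

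*SAP*

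**What the plan says.** SAP 3.6.1 defines duration of IMP exposure as last administration date minus first administration date plus a fixed number of days: "28 days, if the last IMP is prior to Week 24", and "84 days, if the last IMP is on or after Week 24". The result is summarised as a continuous variable, in categories up to more than 48 weeks, and as cumulative participant-years.

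SAP 3.8 brings these rules into the interim: "Analyses methods and conventions described in the other sections of this SAP will be applied for all analyses as applicable". It then adds rules for people still on treatment. The parent bullet reads "Participants without end of treatment visit performed at the time of the cut-off date will be considered as ongoing", and it goes on to treat them as exposed up to that date. The sub-bullets include "Their TE period, treatment period and concomitant medication period will end at the cut-off date" and "Their treatment duration will be derived by considering date of cut-off as last IMP date".

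The interim cut-off is 22 April 2024, described in 3.8 as the date by which all randomized participants had completed at least the Week 24 visit. Extent of exposure is among the listed interim outputs, and 3.8 says the interim efficacy and safety data will be used in discussions with health authorities.

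**The concern.** The 28 or 84 days in 3.6.1 stand for the dosing interval covered by a real injection. Section 3.8 replaces the date of the last real injection with the cut-off date, which in general is not an injection date. It does not say that the added interval is then dropped. Since those still on treatment have reached Week 24, the 84-day branch is the one that applies, and the formula credits 12 weeks that nobody has yet observed.

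At stake is the interim exposure table. Its mean and median durations, its categories and its participant-years would all be too high, in a table intended for regulators. Adverse events starting after the cut-off are excluded, so the safety numerator stops at the cut-off while this measure of time at risk runs past it.

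**Working it through.** **Inputs.** First dose on Day 1; target days 141 (Week 20) and 337 (Week 48) from the analysis-window tables in SAP Appendix 4 (5.4); a 60-week treatment period with the last dose at Week 48 (SAP 1.1); add-ons of 28 and 84 days (SAP 3.6.1); cut-off 22 April 2024 (SAP 3.8); first randomization 14 July 2022 (SAP version history).

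**Step 1: the formula works after a real injection.**
- Completer, last dose Week 48: (337 − 1) + 84 = 420 days = 60.0 weeks, which reproduces the planned treatment period.
- Last dose Week 20: (141 − 1) + 28 = 168 days = 24.0 weeks, also as expected.

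**Step 2: substitute the cut-off for the last dose.** For someone ongoing at Week *w* ≥ 24:

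duration = (cut-off − first IMP) + 84 days = *w* + 12 weeks.

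| Ongoing at | Capped at cut-off | Rules as written | Excess |
|---|---|---|---|
| Week 24 | 24 weeks | 36 weeks | +50% |
| Week 30 | 30 weeks | 42 weeks | +40% |
| Week 48 | 48 weeks | 60 weeks | +25% |
| Week 59 | 59 weeks | 71 weeks | +20% |

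The excess is always 84 days (83 if the cut-off day itself counts as exposed). Anyone ongoing past Week 48 is credited with more than a completer. A participant at Week 30 moves from the >24 to ≤36 week category into the >36 to ≤48 week category.

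**Step 3: participant-years.** 84 / 365.25 = 0.23 per ongoing participant. The documents do not give the number ongoing. If it lay between 100 and 400, the total excess would be about 23 to 92 participant-years.

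**Step 4: illustrative share of total exposure.** Assumptions not in the documents: uniform accrual from 14 July 2022 to 6 November 2023 (168 days before the cut-off), and no dropout. Follow-up at the cut-off then runs uniformly from 168 to 648 days, a span of 480 days.
- Share ongoing (under 420 days): (420 − 168) / 480 = 0.525, with mean true exposure (168 + 420) / 2 = 294 days.
- Mean true exposure overall: 0.525 × 294 + 0.475 × 420 = 353.9 days.
- Excess: 0.525 × 84 = 44.1 days; 44.1 / 353.9 = 12%.
- Replacing uniform accrual by front-loaded or back-loaded power curves (cumulative accrual proportional to time to the power 0.5 or 2) gives ratios of 1.069 and 1.209, so 7% to 21%.
- Under uniform accrual, the >48 week category rises from (648 − 336) / 480 = 65% to (648 − 252) / 480 = 82.5%. The >24 to ≤36 week category falls from (252 − 168) / 480 = 17.5% to zero.

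**The case against.** The strongest reply is that the intent is plain. The parent bullet says these people "will be considered as ongoing and exposed up to the cut-off date", the sub-bullets follow from it, and other conventions carry over only where applicable. A sensible programmer might drop the add-on. That is fair, and it makes this an internal contradiction with a clear intended reading. It does not remove the defect: no readable sentence drops the 84 days, and 3.6.1 holds the only visible formula with a last-dose date into which the cut-off could be put. The difference between treatment duration (3.8) and duration of IMP exposure (3.6.1) does not help either, because 3.6.1 uses both kinds of term for one quantity.

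Second, the substitution is not the sole cause. With the actual last dose, the ordinary formula can itself overrun the cut-off by up to 84 days. With on-time dosing at Weeks 24, 36 and 48 and follow-up spread evenly between doses, that is about 42 days on average. The substitution adds the time since the last injection. This stands, and it is why the remedy needs a cap as well.

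Third, scope. This is an administrative interim with no alpha spent (Protocol 9.3, SAP 3.8), and the excess per ongoing participant is the same in every arm, so no material between-arm distortion is shown. That stands too.

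A reader might also infer that anyone who died, withdrew or was lost without an end-of-treatment visit is counted as exposed to the cut-off. The documents do not establish this. Another sub-bullet of 3.8 defines ongoing as neither having completed nor prematurely discontinued, although it names only the disposition summary. Protocol 7.1.1 also gives permanent discontinuers an early visit with the end-of-treatment assessments. What remains is a question of which test governs, worth a clarifying sentence.

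**Conclusion.** The point holds for the rules as written. Each ongoing participant at or past Week 24 is credited with 84 days (0.23 participant-years) beyond the cut-off, contrary to the SAP's own statement that exposure and the treatment period end there. That figure needs no accrual assumption. One edge case is a Week 24 visit held slightly early and falling on the cut-off, which could be read into the 28-day branch. The totals of about 12%, or 7% to 21%, rest on assumed accrual and no dropout and are only illustrative.

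The visible effect is limited to the interim exposure summary: duration statistics, categories and participant-years. A reader might infer that interim adverse event rates are understated. Any rate using this denominator would be too low, but no exposure-adjusted rate appears in the readable text and the adverse event section is redacted, so that consequence is conditional. Efficacy is not affected: the offset in the exacerbation model (SAP Table 2) is observation duration. Dose counts and compliance use recorded administrations. The final analysis does not use the substitution, and its formula returns 60 weeks for a completer. This should be corrected before the interim exposure tables are run, but it does not threaten the trial's conclusions.

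**What to change.** In SAP 3.8, replace the treatment-duration sub-bullet with: *For ongoing participants, treatment duration = cut-off date − first IMP date + 1, with no 28- or 84-day add-on.* Add: *For all other participants, interim exposure is capped at the cut-off date.* The cap covers people who stopped shortly before the cut-off, whose last actual dose plus 84 days would otherwise run past it.

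As a clarification only, state that the test of having neither completed nor prematurely discontinued governs the exposure and treatment-emergent period rules as well as the disposition summary.

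The cost is two or three sentences and a line of derivation code. Reported interim exposure becomes smaller and agrees with the periods already set to end at the cut-off. No data collection, efficacy analysis or final exposure derivation changes.
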